### Patient follow-up after treatment termination

After a maximum of 12 cycles midostaurin maintenance, patients will be followed up for additional 9 months. If patients stop study treatment or maintenance prematurely, i.e. before having completed 12 cycles of midostaurin maintenance, patients will be followed up until 25 months after study entry.

## 7.2 Dose Modifications

### 7.2.1 Midostaurin Dose Modifications

7.2.1.1 Midostaurin induction and consolidation therapy dose modifications for hematologic toxicity There will be no dose modifications for hematologic toxicity due to midostaurin during induction and consolidation therapy.

7.2.1.2 Midostaurin induction and consolidation therapy dose modifications for non-hematologic toxicity

There will be no dose modifications for any grade 1 or 2 non-hematologic toxicity.

### Cardiac Toxicity

- For QTc interval >450 msecs and ≤ 470 msecs, check magnesium and potassium levels and correct any abnormalities. If possible, stop any medications that may prolong the QTc interval. Continue midostaurin at the same dose.
- For QTc interval > 470 msecs and ≤ 500 msecs, check magnesium and potassium levels and correct any abnormalities. If possible, stop any medications that may prolong the QTc interval. Decrease midostaurin to 50 mg once daily for the remainder of the cycle. Resume midostaurin at the initial dose in the next cycle provided that QTc interval improves to ≤ 470 msecs at the start of that cycle. Otherwise continue midostaurin 50 mg once daily.
- For QTc interval > 500 msecs, check magnesium and potassium levels and correct any abnormalities. Hold or interrupt midostaurin for the remainder of the cycle, and, if possible, stop any medications that may prolong the QTc interval. If QTc improves to ≤ 470 msecs just prior to the next cycle, resume midostaurin at the initial dose. If QTc interval is not improved in time to start the next cycle do not administer midostaurin during that cycle. Midostaurin may be held for as many cycles as necessary until QTc improves.
- Missed doses of midostaurin will not be made up.

### Pulmonary Toxicity

For ≥ grade 3 pulmonary infiltrate, interrupt midostaurin for the remainder of the cycle.
 Resume midostaurin at the same dose when infiltrate resolves to ≤ grade 1.

• Missed doses of midostaurin will not be made up.

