#### Study 2104:

Study 2104 core was a Phase I study of PKC412 in 20 relapsed, refractory or de novo elderly patients otherwise ineligible for chemotherapy, with documented FLT3 mutated AML Patients received PKC412 at a daily dose of 75 mg three times a day. Fourteen of the 20 patients (70%) had  $a \ge 50\%$  decrease in peripheral blood blast counts, and of these, five patients (25%) had  $a \ge 50\%$  decrease in bone marrow blast counts. One patient had a prolonged CR for 285 days by Cheson criteria [17]. Autophosphorylation of FLT3 in responding patients blasts was inhibited by >90% by day 3 [18].

Study 2104E (extension) was an amendment to Study 2104 core, designed to include up to an additional 100 patients with either FLT3WT or FLT3mut AML, tested at lower doses of PKC412 at either 50 mg BID or 100 mg BID. Clinical and biologic activity in 35 additional FLT3 mutated patients treated at these doses was comparable to that of patients treated at the higher dose of 75 mg three times a day in Study 2104 Core. FLT3 mutated patients treated at doses of 50 and 100 mg bid had a similar incidence of biologic activity as measured by >50% peripheral blast reduction (61%, 71%) and >50% bone marrow blast reduction (28% and 23%) respectively. One PR was observed in a FLTmut patient treated on 100 mg bid. Of the 57 patients that were FLT3 WT, biological activity was also seen, although less frequently than in FLT3 mutated patients, at 47% and 33% for 50 mg bid and 100mg bid regimens, respectively. No CRs or PRs were observed in the FLT3WT patients.

PKC412 was generally well tolerated. The most common toxicities were Grade 1/2 nausea (48%), vomiting (41%), diarrhea (26%) and fatigue (7%). In Study 2104 Core, there were 2 patients dying of pulmonary failure of unknown etiology. In Study 2104E, there were 2 additional cases of Grade 4 pulmonary edema and/or infiltrates in patients on antifungal azole medications known to be potent CYP3A4 inhibitors; these patients had substantially high PK levels than others without this toxicity. Because of this observation, patients were subsequently no longer allowed on antifungal azoles, and clear chest X rays were made inclusion criteria. Once these changes were implemented, severe pulmonary events with no known aetiology did not occur further.

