## 7.2.2 High-Dose Cytarabin Consolidation Therapy Dose Modifications

Contributions of concomitant medications to neurotoxicity should be assessed and other medications discontinued if possible.

For neurotoxicity  $\geq$  grade 2 due to high-dose cytarabine during consolidation therapy, discontinue high-dose cytarabine for the remainder of the cycle. High-dose cytarabine may be considered at the next consolidation therapy cycle with a dose modification from 3 g/m^2 to 2 g/m^2 if the toxicity has resolved to  $\leq$  grade 1.

For a second occurrence of neurotoxicity  $\geq$  grade 2, high-dose cytarabine should be permanently discontinued.

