## 7.3 Concomitant Treatment/Medication

There is no restriction for any medically necessary concomitant treatments or medications. Physicians should be aware that midostaurin is a competitive inhibitor of CYP3A4/5. Studies also show CYP3A4 is the major human p450 enzyme catalyzing biotransformation of midostaurin. Thus, co-administration of drugs which are potent inducers (e.g. phenytoin) or, especially, potent inhibitors (e.g. itraconazole) of this isoenzyme could decrease or increase midostaurin concentrations, and, potentially, decrease the effectiveness or increase toxicity, respectively. A list of agents that may have potential drug interactions is given in appendix 2.

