### 8.4.2 Toxicities

When given as a single agent, doses of up to 300 mg per day (100 mg three times a day) of midostaurin have been used. A dose of 225 mg per day (75 mg three times a day) was originally selected for phase II studies. The adverse events most frequently reported and considered related to midostaurin were nausea, vomiting, and fatigue. In most cases vomiting occurred within an hour of taking midostaurin and subsided when treatment was withdrawn. Treatment with antiemetics was tried with variable success. Other adverse events commonly reported and suspected to be related to midostaurin include headache, and diarrhea. Serious adverse events considered related to midostaurin include diarrhea, vomiting, nausea, anorexia, anemia, leukopenia, elevated liver transaminase levels, and pulmonary edema.

The tolerability (MTD) of midostaurin in combination with chemotherapy is somewhat lower than that seen with single agent midostaurin due to additive toxicity of nausea and vomiting in the combination regimens.

Reversible elevations in transaminases and bilirubin have been reported with midostaurin, including at least three patients with grade 3 elevations at the 50 mg BID dose. To date, there have been no associated pathological changes reported. Transient increase in serum amylase of unknown significance has been observed in four oncology patients. Rash (grad 3 / 4) also was reported in at least one patient.

Pulmonary toxicity including fatal pulmonary events have been described in patients receiving midostaurin. It hast been suggested that pulmonary toxicity may be associated with co-administration of azole antifungal drugs and resultant inhibition of CYP3A4.

Two cases of hyperthyroidism were reported as serious adverse events in two patients treated with midostaurin in combination with imatinib for imatinib-resistant gastrointestinal tumors (GIST). Additionally, there were two adverse events of grade 1 and grade 2 hyperthyroidism as well as six events of asymptomatic thyroid function test lab changes reported in the same study. It is felt that theses events were possibly related to the combination study medication although the mechanism

is not clear. To date, trials with midostaurin monotherapy have not yielded any reports of hyperthyroidism or similarly mentioned thyroid function test abnormalities.

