### 8.4.3 Drug interactions

Midostaurin is metabolized by CYP3A4 to active compounds. As described in section 7.3, potent CYP3A4 inhibitors are thought to represent the most significant potential for drug interactions with midostaurin.

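### The lung-toxicity rules restart midostaurin at the same dose without asking whether a potent CYP3A4 inhibitor is still being taken

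*Protocol*

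**What the plan says.** **The lung rules.** Protocol 7.2.1.2 and 7.2.1.4 give the same instruction. At a grade 3 or higher pulmonary infiltrate, midostaurin stops for the rest of that cycle. Then: "Resume midostaurin at the same dose when infiltrate resolves to" grade 1 or less. Missed doses are not made up. Co-medication is not mentioned in either place.

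**What the protocol says about lung toxicity and co-medication.** Section 2.2.2 (Study 2104) reports, for the extension study, "2 additional cases of Grade 4 pulmonary edema and/or infiltrates in patients on antifungal azole medications known to be potent CYP3A4 inhibitors", and adds that "these patients had substantially high PK levels than others without this toxicity". Azoles were then disallowed in that study, and a clear chest X-ray became an inclusion criterion. Section 8.4.2 mentions fatal pulmonary events and a suggestion that "pulmonary toxicity may be associated with co-administration of azole antifungal drugs and resultant inhibition of CYP3A4". Section 8.4.3 says that "potent CYP3A4 inhibitors are thought to represent the most significant potential for drug interactions with midostaurin".

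**General co-medication rule.** Section 7.3 opens: "There is no restriction for any medically necessary concomitant treatments or medications". It then alerts physicians to CYP3A4 inducers and, with more emphasis, to potent inhibitors. It names itraconazole and refers to the list in Appendix 2.

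**Other dose-modification rules.** The QTc rules include "If possible, stop any medications that may prolong the QTc interval". The high-dose cytarabine rule in 7.2.2 includes "Contributions of concomitant medications to neurotoxicity should be assessed and other medications discontinued if possible".

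**The concern.** The protocol names a suspected mechanism for severe lung toxicity: CYP3A4 inhibition raises midostaurin exposure. Its rule for that toxicity then acts on midostaurin alone. A patient whose infiltrate clears while still taking a potent inhibitor is, under the rule as written, restarted at the same dose. That could reproduce the raised exposure described for the two earlier cases.

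The timing adds to this. Appendix 2 lists antifungals and antibacterials such as itraconazole and clarithromycin. As a clinical judgement, not something the protocol states, an infiltrate may itself prompt drugs of this kind. The event is therefore when a medication check is most useful. What is at stake is the safety of the individual patient at rechallenge.

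**Working it through.** No stated figure needs reproducing. The check is a comparison of rules plus a short calculation of the time off drug.

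**1. Is there a co-medication step in the rule?**

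| Rule | Section | Co-medication step |
|---|---|---|
| Lung infiltrate, induction and consolidation | 7.2.1.2 | No |
| Lung infiltrate, maintenance | 7.2.1.4 | No |
| QTc, three bands, induction and consolidation | 7.2.1.2 | In all 3 |
| QTc, three bands, maintenance | 7.2.1.4 | In all 3 |
| Cytarabine neurotoxicity | 7.2.2 | Yes |

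The step is in 0 of 2 lung rules, in 6 of 6 QTc bands and in the neurotoxicity rule. The rules for other grade 3/4 non-hematologic toxicity also lack it, but the protocol states no comparable co-medication link for those toxicities.

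**2. Does another section supply the action?**

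- Sections 7.3, 8.4.2, 8.4.3 and Appendix 2 inform. None says what to do with an inhibitor after a lung event.
- Section 6.3 allows withdrawal if continuing would harm the patient. It requires withdrawal for unacceptable toxicity or a maintenance interruption of more than 28 days. This covers patients who stop, not those who recover and restart.
- The DSMB (section 14) reviews serious events and can recommend amendments. That is oversight of the trial, not a step at the individual restart.

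**3. Does the time off drug settle the matter?**

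Chemotherapy cycles: the last midostaurin day is 21. The next cycle starts no earlier than four weeks after the start of the previous one, that is on day 29. Its day 8 is then day 36. Days 22 to 35 are free of drug, so the gap is at least 35 − 22 + 1 = 14 days. The earliest start of maintenance is also day 36, which gives the same minimum.

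Maintenance: dosing is continuous in 28-day cycles, and the next cycle starts on day 29. If drug is stopped from day d, the rest-of-cycle interruption is 29 − d days:

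- d = 1: 28 days
- d = 14: 15 days
- d = 21: 8 days
- d = 28: 1 day

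Restart also requires the infiltrate to be grade 1 or less, so the shortest values are lower limits and not typical. Whatever its length, the gap removes midostaurin and leaves the inhibitor in place.

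**4. How strong is the evidence for the link?**

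- There are two grade 4 cases on azoles, under single-agent midostaurin.
- The extension study used 50 or 100 mg twice daily, a range that includes this trial's 50 mg twice daily. The doses of these two patients are not given.
- The azole ban and the chest X-ray criterion were introduced together. The later absence of severe lung events of unknown cause cannot be credited to either one.
- The numbers treated before and after those changes are not given, so no event rate can be calculated.

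**The case against.** The strongest case against is that nothing here is misstated or contradictory. The lung rule is clear and in some respects stricter than its neighbours. It applies whatever the cause of the infiltrate and halts drug until at least the next cycle, whereas the rules for other grade 3/4 toxicity require a possible relation to midostaurin. In maintenance it demands recovery to grade 1 or less, where the other-toxicity rule accepts grade 2. Investigators are told of the azole link in 8.4.2 and warned about potent inhibitors in 7.3, so a competent physician would check anyway. All of this is fair, and it limits the weight of the point. It does not supply the missing action. With 25 planned centres and 18 patients, a site may meet such an event rarely and rely on the written rule.

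A reader might infer that the QTc and neurotoxicity rules make the omission an internal inconsistency. They do not. Those rules target drugs that add directly to the toxicity, while a CYP3A4 inhibitor matters here through midostaurin exposure, and midostaurin has already been stopped. They are loose parallels only.

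A reader might also infer that the risk lies mainly in maintenance, because most planned midostaurin days fall there. A share of dosing days measures neither lung events nor inhibitor use. In addition, section 2.2.2 reports that levels fall with continuous dosing through autoinduction and partly recover after a break. The direction of the net effect at restart is therefore not established.

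Finally, a proposal qualified by 'if possible' still lets a patient who needs an azole restart at the same dose. That is true. The sentence makes the check explicit but does not guarantee removal of the inhibitor.

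**Conclusion.** The point holds as a modest patient-safety improvement. Both lung rules direct a same-dose restart with no look at CYP3A4 inhibitors, although the protocol itself reports a suspected link, and no other section sets an action before restart.

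Its size cannot be expressed as a rate. It rests on two cases with unstated individual doses and on an association described only as suggested. It also assumes that some patients will still be taking a potent inhibitor at restart. Section 7.3 permits this when medically necessary, but the documents do not say how often it would occur.

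A reader might go further and conclude that azoles should be banned, as in the extension study, or that the ban is what ended the lung events. The documents support neither: two changes were made at once, and patients with AML may need an azole. Nor is it right to say that the protocol leaves inhibitors without caution, because 7.3 warns about them explicitly.

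The sample size of 18, the one-sided 5% level and the 13-of-18 decision rule are unaffected.

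**What to change.** Add one sentence to the pulmonary toxicity rule in both 7.2.1.2 and 7.2.1.4:

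*Review concomitant CYP3A4 inhibitors; if possible, stop or replace any potent inhibitor before midostaurin is resumed.*

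No broader restriction in 7.3 is needed.

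The cost is one sentence in two places. No new examination or data item is required, because the schedule in 7.4 already records concomitant medication in the chemotherapy cycles and during maintenance. The downside is that a suitable alternative antifungal may not always exist, which is why the sentence says 'if possible' and leaves the decision with the treating physician.

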### Other Non-Hematologic Toxicity

If a patient experiences other grade 3 / 4 non-hematologic toxicity considered at least possibly related to midostaurin, the midostaurin will be interrupted until toxicity resolves to  $\leq$  grade 1. If the toxicity resolves prior to day 21, then restart at same dose to complete current cycle. Missed doses of midostaurin will not be made up.

## 7.2.1.3 Midostaurin dose modifications for hematologic toxicity during maintenance treatment

In the presence of grade 4 neutropenia during continuation therapy, midostaurin must be held until ANC  $\geq 1000/\mu$ L. Once ANC  $\geq 1000/\mu$ L, then resume midostaurin at the previous dose. If neutropenia persists for more than two weeks, then discontinue midostaurin protocol therapy.

7.2.1.4 Midostaurin therapy dose modifications for non-hematologic toxicity during maintenance

### Cardiac Toxicity

- For QTc interval >450 msecs and ≤ 470 msecs, check magnesium and potassium levels and correct any abnormalities. If possible, stop any medications that may prolong the QTc interval. Continue midostaurin at the same dose.
- For QTc interval > 470 msecs and ≤ 500 msecs, check magnesium and potassium levels and correct any abnormalities. If possible, stop any medications that may prolong the QTc interval. Decrease midostaurin to 50 mg once daily for the remainder of the cycle. Resume midostaurin at the initial dose in the next cycle provided that QTc interval improves to ≤ 470 msecs at the start of that cycle. Otherwise continue midostaurin 50 mg once daily.
- For QTc interval > 500 msecs, check magnesium and potassium levels and correct any abnormalities. Hold or interrupt midostaurin for the remainder of the cycle, and, if possible, stop any medications that may prolong the QTc interval. If QTc improves to ≤ 470 msecs just prior to the next cycle, resume midostaurin at the initial dose. If QTc interval is not improved in time to start the next cycle do not administer midostaurin during that cycle. Midostaurin may be held for as many cycles as necessary until QTc improves.
- Missed doses of midostaurin will not be made up.
- Dose modifications for QTc are for the remainder of the cycle.

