### 6.3 Removal of patients from study

All patients reaching a primary efficacy endpoint of the trial (event) will discontinue study treatment and will be followed up until 25 months after study entry. The following events will lead to discontinuation of study treatment:

- Primary refractory disease, defined as failure to achieve a CR/CRi five weeks after the beginning of the second induction therapy
- Hematological relapse from CR/CRi
- Death from any cause

A patient who withdraws is one who discontinues participation in a clinical study for any reason. Patients may be withdrawn from the trial for the following reasons:

- At their own request or at the request of their legally acceptable representative
- If, in the investigator's opinion, continuation in the study would be detrimental to the patient's well-being
- At the specific request of the sponsor

Patients must be withdrawn also for the following reasons:

- In case of unacceptable toxicity or progressive disease
- In case of substantial non-compliance with the requirements of the study
- Positive beta-HCG test consistent with pregnancy. Pregnancy will be reported along the same time lines as a serious adverse event
- Use of illicit drugs or other substances that may, in the opinion of the investigator, have a reasonable chance of contributing to toxicity or otherwise skewing results
- Development of an intercurrent illness or situation which would, in the judgment of the investigator, affect assessments of clinical status and study endpoints to a significant degree
- Development of a second cancer that requires treatment
- Patient is lost to follow-up
- Period of > 64 days between the start of the last consolidation cycle and beginning of maintenance treatment
- Interruption in study drug administration for a period longer than 28 consecutive days during maintenance treatment

Relevant visit data will be entered into the CRF, and any unused study medication will be accounted for and returned for all subjects entered into the trial even if for a brief period of time. Subjects who discontinue study treatment will have relevant information completed and recorded in the CRF and medical record. All subjects who discontinue because of adverse events or clinical laboratory abnormalities should be followed up until they recover or stabilize and the subsequent outcome recorded.

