### Midostaurin maintenance

Patients who continue in complete remission (by bone marrow aspiration and blood evaluation) after three cycles of consolidation therapy will receive midostaurin maintenance therapy. If, in the opinion of the investigator, the clinical condition of a patient does not allow a third cycle of MidoHiDAC, the SAL central study office should be contacted for medical advise. If the LKP agrees that the risk of serious adverse events is too high in case of a third MidoHiDAC application, midostaurin maintenance may commence after two cycles of MidoHiDAC.

Prior to initiation of midostaurin maintenance therapy, all significant acute toxicity from consolidation therapy must have resolved to grade 2. Maintenance will begin after hematologic recovery (ANC  $\geq$  1000/ µL, platelet count  $\geq$ 50,000/µL) from remission consolidation and no sooner than 14 days after the last midostaurin application in the last cycle of MidoHiDAC, i.e. earliest on day 36 after the beginning of the last cycle of MidoHiDAC. Maintenance treatment must be started before day 64 after the beginning of the last cycle of MidoHiDAC, i.e. patients who cannot start maintenance treatment until 64 days after the beginning of the last cycle of MidoHiDAC, i.e. patients who cannot start maintenance treatment until 64 days after the beginning of the last cycle of MidoHiDAC, i.e. patients who cannot start maintenance treatment until 64 days after the beginning of the last cycle of the last cycle of MidoHiDAC will stop study treatment and will be followed up until 25 months after study entry.

Maintenance treatment consists of continuous midostaurin application for 12 cycles with 28 days per cycle:

Midostaurin50 mg (2 capsules) p.o. twice dailydays 1-28Start of new maintenance cycle on day 29

Midostaurin 50 mg (two 25 mg capsules) is given twice a day by mouth on days 1-28. Patients should take their doses at approximately the same time each day, and approximately 12 hours should elapse between the morning and evening doses. Each daily dose should be given with food and a glass of water (approx. 240 ml). Patients should be instructed to swallow capsules whole and not chew capsules. If vomiting occurs, no re-dosing is allowed before the next scheduled dose.

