### Other Grade 3 / 4 Non-Hematologic Toxicity

- For other grade 3 / 4 non-hematologic toxicities that are considered to be at least possibly related to midostaurin, interrupt midostaurin. Resume midostaurin at the same dose when toxicity resolves to ≤ grade 2. If midostaurin is held for more than 28 days, then discontinue midostaurin continuation therapy.
- Missed doses of midostaurin will not be made up.

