## Other Grade 1 / 2 Non-Hematologic Toxicity

- Persistent grade 1 or 2 toxicity during continuation therapy that patients may deem unacceptable may prompt a drug holiday for as many as 28 days. No drug holidays longer than 28 consecutive days will be allowed.
- Missed doses of midostaurin will not be made up.

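### In maintenance, the QTc rule in section 7.2.1.4 permits holds over several cycles, but section 6.3 requires withdrawal after more than 28 consecutive days off drug and makes no QTc exception (minor)

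*Protocol*

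**What the plan says.** Section 7.2.1.4 (Cardiac Toxicity) covers QTc above 500 ms in maintenance. Midostaurin is stopped for the rest of the current cycle. If QTc has come down to 470 ms or less just before the next cycle, the drug is restarted at its starting dose. Otherwise: "If QTc interval is not improved in time to start the next cycle do not administer midostaurin during that cycle". The next sentence reads: "Midostaurin may be held for as many cycles as necessary until QTc improves".

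Section 6.3 has a list headed "Patients must be withdrawn also for the following reasons". One item is: "Interruption in study drug administration for a period longer than 28 consecutive days during maintenance treatment".

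Section 7.1 fixes the cycle length: "Maintenance treatment consists of continuous midostaurin application for 12 cycles with 28 days per cycle".

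Elsewhere in section 7.2.1.4 the limit of section 6.3 is repeated. For other grade 3/4 non-hematologic toxicity: "If midostaurin is held for more than 28 days, then discontinue midostaurin continuation therapy". For other grade 1/2 toxicity: "No drug holidays longer than 28 consecutive days will be allowed".

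**The concern.** Both rules govern the same phase and the same event, an interruption of midostaurin in maintenance. One tells the site that a QTc hold may run over as many cycles as it takes. The other says that a patient off drug for more than 28 days in a row must be withdrawn. Section 6.3 does not exempt QTc holds, section 7.2.1.4 does not refer to the 28-day limit, and the protocol states no order of precedence.

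The stake is the handling of a patient whose QTc recovers after a skipped cycle. A site working from the dose-modification section would probably restart 50 mg twice daily. A site working from the removal criteria would stop midostaurin for good. The protocol plans 25 centres, and re-challenge after QTc above 500 ms is a cardiac safety decision that should rest on one stated rule.

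**Working it through.** The plan gives no figure on this point to reproduce. The check is a count of days, followed by a comparison of the rules.

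**Inputs**
- Maintenance cycle: 28 days of continuous dosing, with the next cycle starting on day 29 (section 7.1).
- QTc above 500 ms: hold to the end of the current cycle, then omit whole cycles until QTc improves (section 7.2.1.4).
- Withdrawal limit: more than 28 consecutive days off drug (section 6.3).

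**Formula.** Let k be the dose-days missed in the triggering cycle (0 to 28) and m the number of whole cycles then omitted. Consecutive days off drug = k + 28m.

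| Omitted cycles m | Days off drug | Over 28 days? |
|---|---|---|
| 0 | 0 + 0 = 0 to 28 + 0 = 28 | Never |
| 1 | 0 + 28 = 28 to 28 + 28 = 56 | Yes for k = 1 to 28; exactly 28 for k = 0 |
| 2 | 0 + 56 = 56 to 28 + 56 = 84 | Always |

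The case k = 0 arises only if the prolonged QTc is found after the last dose of a cycle. If the hold is counted from at least one missed dose-day, one omitted cycle gives 29 to 56 days and is always over the limit. The two counts differ only in that edge case.

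A hold confined to the triggering cycle thus never conflicts with section 6.3. With an omitted cycle, the only case that stays within the limit is one omitted cycle with no dose-day missed before it.

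**Comparison with neighbouring rules**
- Sections 6.3 and 7.2.1.4 agree for other grade 3/4 and grade 1/2 toxicity, because both repeat the 28-day limit.
- Grade 4 neutropenia has its own, shorter limit: midostaurin is discontinued if neutropenia lasts more than two weeks (section 7.2.1.3).
- The pulmonary rule in maintenance states no limit, but it does not expressly allow holds over several cycles, so it sits under section 6.3 without conflict.
- The same QTc sentences appear for induction and consolidation (section 7.2.1.2). They cause no conflict there, because the 28-day item is limited to maintenance.

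QTc in maintenance is the only toxicity with an open-ended permission that meets the 28-day item.

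**Effect on the primary analysis.** An interruption of drug is not an event under the definitions in sections 9.1 and 13.2.1. Section 7.1 follows patients who stop early to month 25 from study entry. It treats another item of the same section 6.3 list, the 64-day limit for starting maintenance, as a stop of treatment with continued follow-up. The sample size of 18 and the cut-off of 13 in section 13.3 do not depend on the hold rule.

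**The case against.** The strongest reply is that the two sections can be obeyed together. The QTc sentence is permissive and section 6.3 is mandatory, so a site may hold while QTc is prolonged and withdraw the patient once the gap passes 28 days. Part of this stands. A reader might infer that the two sections give directly opposite orders, and the text does not go that far. The express order to restart is tied to recovery just before the next cycle, which is the case with no omitted cycle. Restart after an omitted cycle is implied by the words about holding until QTc improves; it is not ordered. The reply still does not remove the conflict. If section 6.3 is a silent cap, the permission for several cycles has almost no effect, although it stands in the section that sites use for dosing.

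A second reply is that the QTc rule is a deliberate special rule, since the repeated 28-day limits stand under headings for other toxicities. That may be the intent, but then section 6.3 lacks the exception. The documents do not show which was meant.

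The closing bullet, "Dose modifications for QTc are for the remainder of the cycle", might be read as limiting every QTc hold to the triggering cycle, or as a further contradiction. Neither reading is needed. It reads naturally as saying that each modification runs to the end of the cycle and QTc is then reassessed. It does not settle the question.

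A reader might also infer that withdrawal under section 6.3 ends follow-up and so costs data on the primary endpoint. The follow-up rules in section 7.1 do not support this.

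**Conclusion.** Wrong as written, and minor. In maintenance, a QTc hold that includes an omitted cycle meets the mandatory withdrawal criterion in all but one edge case (28 to 56 days off drug for one omitted cycle, at least 56 for two), while section 7.2.1.4 permits the hold and implies a restart. The count assumes that cycles follow one another without a gap and that an omitted cycle counts as an interruption in the sense of section 6.3.

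The practical effect is limited to re-challenge after QTc above 500 ms and to the maintenance exposure that remains. The documents give no frequency for QTc above 500 ms. At most 18 patients are enrolled and only those still in remission after consolidation enter maintenance, so the number affected is unknown and may be zero. Type I error, power, the decision rule and follow-up for event-free survival are unchanged.

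**What to change.** Keep the hold to the end of the triggering cycle as it stands. Removing it would allow a full-dose restart mid-cycle, soon after QTc above 500 ms, and the conflict does not require that. Then choose one rule.

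**(a) Cap the hold.** In section 7.2.1.4 (maintenance), replace the two sentences quoted above on omitting the next cycle and on holding for several cycles. Suggested content: if QTc is still above 470 ms when the next cycle is due, go on holding and repeat the ECG; the starting dose may be resumed once QTc is 470 ms or less; after more than 28 consecutive days off drug, stop midostaurin permanently and continue follow-up to month 25 from study entry. This matches section 6.3 and the other toxicity rules in section 7.2.1.4. The repeat ECG is needed because scheduled ECGs in maintenance are only monthly (section 7.4).

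**(b) Write the exception.** If longer holds with re-challenge are intended, leave section 7.2.1.4 as it is and exempt QTc holds under that section from the 28-day item in section 6.3.

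**Cost.** The change is a few lines of text and a note to sites, but either option may need a substantial amendment. Under (a), each patient on a prolonged hold needs at least one extra ECG, and restart becomes possible part-way through the following cycle, where the present text omits that cycle entirely. The time left for recovery after the triggering cycle is 28 − k days: 14 if 14 dose-days were missed, and none if all 28 were. A few patients with slow QTc recovery would lose the rest of maintenance. Under (b), those patients are re-challenged after a longer gap.
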